Non-interventional Study Protocol

Document Number:	c19925296-03
BI Study Number:	1245.149
BI Investigational Product(s):	Jardiance® (Empagliflozin)
Title:	Post-authorization safety study in patients with type 2 diabetes mellitus to assess the incidence of ketoacidosis, severe complications of urinary tract infection, volume depletion, and dehydration among patients treated with Empagliflozin or DPP-4 inhibitors in Saudi Arabia
Brief lay title	Post-authorization safety study in type 2 diabetic patients in Saudi Arabia treated with Empagliflozin to assess the incidence of ketoacidosis, severe complications of urinary tract infection, volume depletion, and dehydration
Protocol version identifier:	3.0
Date of last version of protocol:	03 May 2018
PASS:	Yes
EU PAS register number:	EUPAS20025
Active substance:	Jardiance® (Empagliflozin 10mg & 25 mg)
Medicinal product:	Jardiance® film-coated tablets 10mg, 25mg
Product reference:	Empagliflozin 10 mg: 103-68-16 Empagliflozin 25 mg: 104-68-16
Procedure number:	SFDA application no. 17062102 on SCTR
Marketing authorisation holder(s):	Boehringer Ingelheim Saudi Arabia
Joint PASS:	No
Research question and objectives:	NIS with new data collection, with the following aims: Primary outcomes To estimate the incidence of: - Ketoacidosis - Severe urinary tract infections

	
- Volume depletion- Dehydration 
in type 2 diabetes mellitus (T2DM) patients exposed to Jardiance® (Empagliflozin) compared with the incidence in T2DM patients exposed to Dipeptidyl peptidase-4 (DPP-4) inhibitors
 
Secondary outcomes
 
To estimate the risk of each primary outcome with respect to the following definition of exposure: the Ramadan period

Country of study:	Multi-Centre study conducted in Saudi Arabia
Author:	[REDACTED]
Marketing authorisation holder:	Boehringer Ingelheim
MAH contact person:	[REDACTED]
EU-QPPV:	[REDACTED]
Signature of EU-QPPV:	The signature of the EU-QPPV is provided electronically
Date:	23 Sep 2019

2. LIST OF ABBREVIATIONS

ACR	Albumin Creatinine Ratio
ADR	Adverse Drug Reaction
AE	Adverse Event
AESI	Adverse Event of Special Interest
BI	Boehringer Ingelheim
BP	Blood Pressure
CA	Competent Authority
CML	Local Clinical Monitor
CRA	Clinical Research Associate
CRO	Contract Research Organization
CTP	Clinical Trial Protocol
CTR	Clinical Trial Report
DKA	Diabetic ketoacidosis
DMP	Data Management Plan
DPP-4	Dipeptidyl-peptidase 4
E-CRF	Electronic Case Report Form
EDC	Electronic Data Capture
eGFR	Estimated Glomerular Filtration Rate
EU	European Union
EU PAS	European Union electronic register of post-authorization studies
EU-QPPV	European Union-Qualified Person for Pharmacovigilance
FPG	Fasting Plasma Glucose
GCP	Good Clinical Practice
GLD	Glucose lowering drug
GLUT	Glucose Transporter
GPP	Good Pharmacy Practice
HbA1c	Glycated Hemoglobin
HDL-C	High Density Lipoprotein Cholesterol
IC50	Inhibitory Concentration
ICH	International Conference on Harmonisation
IEC	Independent Ethics Committee

IRB	Institutional Review Board
ISF	Investigator Site File
LDL-C	Low Density Lipoprotein Cholesterol
LPVM	Local PV Manager
MAH	Marketing Authorisation Holder Activities
MedDRA	Medical Dictionary for Drug Regulatory Activities
MFDS	The Ministry of Food and Drug Safety
SFDA	Saudi Food & Drug Authority

3. RESPONSIBLE PARTIES

Boehringer Ingelheim (BI) has appointed a Trial Clinical Monitor (TCM), responsible for coordinating all required activities, in order to

- Manage the study in accordance with applicable regulations and internal standard operating procedures (SOPs).
- direct the study team in the preparation, conduct, and reporting of the trial,
- order the materials as needed for the study,
- Ensure appropriate training and information of Local Clinical Monitors (CMLs), Clinical Research Associate (CRAs), and Investigators of Saudi Arabia.

The organization of the study will be done by a Contract Research Organization (██████████) with which the responsibilities and tasks will have been agreed and a written contract filed before initiation of the study. A CML will be appointed responsible for coordinating the activities required in order to manage the study in accordance with applicable regulations and internal SOPs in the countries covered by the respective BI OPU. On-site monitoring will be performed by a CRO appointed by BI.

An Investigator Site File (ISF) containing all relevant study related documentation will be maintained according to local regulations and BI and/or CRO SOPs at each study site. A copy of the ISF documents will also be kept as an electronic Trial Master File (TMF) at BI according to BI and/or CRO SOPs. Documents related to participating physician and other important participants, especially their curricula vitae, will be filed in the TMF.

4. ABSTRACT

Name of company: [REDACTED]			
Name of finished medicinal product: Jardiance®			
Name of active ingredient: Empagliflozin			
Protocol date: 16 Oct 2017	Study number: 1245.149	Version/Revision: 3.0	Version/Revision date: 23 Sep 2019
Title of study:	Post-authorization safety study in patients with type 2 diabetes mellitus to assess the incidence of ketoacidosis, severe complications of urinary tract infection, volume depletion, and dehydration among patients treated with Empagliflozin or DPP-4 inhibitors in Saudi Arabia		
Rationale and background:	According to the local regulations, for some safety concerns, additional pharmacovigilance activities, for instance post-authorization safety studies which are initiated, managed or financed by marketing authorization holders, voluntarily, or pursuant to obligations can be imposed by SFDA. SFDA has requested a non-interventional study (NIS) to provide supplementary data to monitor the safety of Jardiance® (Empagliflozin) in a real-life situation including the Ramadan period.		
Research question and objectives:	
Non-interventional study with new data collection, with the following aims:
 
Primary outcomes
 
To estimate the incidence of:
 
 - Ketoacidosis - Severe urinary tract infections - Volume depletion - Dehydration 
in type 2 diabetes mellitus (T2DM) patients initiating Jardiance® (Empagliflozin) compared with the incidence in T2DM patients initiating Dipeptidyl peptidase-4 (DPP-4) inhibitors
 
Secondary outcomes
 
To estimate the risk of each primary outcome with respect to the following definition of exposure: the Ramadan period
 
Primary and secondary outcomes will be followed up for 1 year from Index date
		

Name of company: [REDACTED]			
Name of finished medicinal product: Jardiance®			
Name of active ingredient: Empagliflozin			
Protocol date: 16 Oct 2017	Study number: 1245.149	Version/Revision: 3.0	Version/Revision date: 23 Sep 2019
Study design:	
This will be non-interventional study with new data collection. The study will use a “new users” design and compare new users of Jardiance® (Empagliflozin) to new users of DPP-4 inhibitors. The index date will be defined as the date on which each identified new user receives the index prescription for Jardiance® (Empagliflozin) or a DPP-4 inhibitor.
 
Number of recruited patients will be comparable in each group within a given timeframe (i.e. each site will ensure to recruit similar number of patients for each group according to assigned blocks of enrolment)
 
Propensity scores based on information prior to the index date will be used to account for potential confounding.
 
Patients will be follow-up for 12 months after index date.
		
Population:	
Patients diagnosed with T2DM in Saudi Arabia
 
The study population will include patients aged at least 18 years and diagnosed with T2DM in Saudi Arabia and who will initiate Jardiance® (Empagliflozin) treatment during the study period and who have not used other SGLT2 inhibitors during the previous 12 months.
 
Patients switching to or adding Jardiance® (Empagliflozin) to other antidiabetic medications will be compared to patients switching to or adding comparator treatment on same background therapy. This modification of a “new-user” design is an appropriate method for studying second-line therapies in chronic conditions.
 
The comparator groups will include new users of DPP-4 inhibitors. The same inclusion and exclusion criteria will be applied.
 
  Patients with a confirmed diagnosis of type 1 diabetes before or after the index date will not be included in the study.  Patients prescribed fixed-dose combinations of SGLT2 inhibitors with DPP-4 inhibitors will be excluded. 		

Name of company: [REDACTED]			
Name of finished medicinal product: Jardiance®			
Name of active ingredient: Empagliflozin			
Protocol date: 16 Oct 2017	Study number: 1245.149	Version/Revision: 3.0	Version/Revision date: 23 Sep 2019
Variables:	
Covariates:
 
Variables potentially associated with outcomes of interest—such as Sociodemographic variables including age, sex, concomitant medications; will be identified for all cohort members prior to and including the index date. Severity of T2D will be assessed by HbA1c values concomitant diagnoses and duration since the first diagnosis, when available. These and other variables that can differ by exposure group will be considered for inclusion as predictors in the logistic regression models used to generate the propensity scores.
 
Propensity scores will be used in the analysis to quantify the probability of receiving Jardiance® (Empagliflozin) at the index date for new users of both Jardiance® (Empagliflozin) and DPP-4 inhibitors. At the index date, cohort members will also be classified by indicator variables on the calendar time of cohort entry (by quarter) whether the index treatment (Empagliflozin or DPP-4 inhibitor) was added to existing medication (adding on), or if the index treatment was initiated as a replacement for another GLD (switching from the existing GLD to Jardiance® (Empagliflozin) or DPP-4 inhibitor, and whether this treatment was received as monotherapy or as dual or triple therapy.
 
A variable indicating whether or not patients were receiving insulin at the index date will also be created.
		
Data sources:	
The investigator will be asked to successively write in the case report forms (e-CRFs) from the subject who was initially administered the drug following the study start date to the requested number of subjects without omission. Data on the period preceding the index date will be collected at the time of the first survey.
 
Prior to initiation of the study, written contract shall be concluded, and this contract shall be concluded with the head of the site or the investigator with his/her consent. Non-Interventional study with new data collection
		
Study size:	
Based on the requirements of SFDA, the sample size will be 1500 patients overall, 750 patients in each group DPP4i and Empagliflozin. The recruitment process will be adjusted in each site accordingly.
		

Name of company: [REDACTED]			
Name of finished medicinal product: Jardiance®			
Name of active ingredient: Empagliflozin			
Protocol date: 16 Oct 2017	Study number: 1245.149	Version/Revision: 3.0	Version/Revision date: 23 Sep 2019
Data analysis:	
For the incident users of Jardiance® (Empagliflozin) and of DPP4i, analysis will be performed using the “as-treated” (AT) approach. This corresponds to censoring individuals who discontinue use of the index drug, i.e. either switch from the index drug to any other of the index drug Jardiance® (Empagliflozin) or DPP-4 inhibitor during follow-up or stop using the index drug.
 
For the assessment of the primary and secondary objectives, the main data analysis will be conducted in two stages:
 
 - Construction of the propensity score (PS) by modelling the exposure Jardiance® (Empagliflozin) vs. DPP-4 inhibitor - Estimation of the effect of exposure to Jardiance® (Empagliflozin) on the ketoacidosis, severe urinary tract infections, volume depletion and dehydration compared to those exposed to DPP-4 inhibitor. 
Additional sensitivity analyses will be performed to validate the robustness of alternative definitions of outcome, exposure, covariates and reduction of bias due to matching.
 
The following estimates and comparison will be generated:
 
 - Crude and adjusted incidence rates of each of the outcomes among Jardiance® (Empagliflozin) new users and among DPP-4 inhibitor new users. Incidence rates will be reported as point estimates (in cases per 1,000 person-years) and 95% confidence intervals (CIs). - Summary IRRs, after adjusting (via stratified Mantel-Haenszel analysis) for propensity score deciles and calendar year, among Empagliflozin new users versus DPP-4 inhibitor new users - Adjusted IRRs for each of the outcomes will be the main effect estimates of interest. Adjusted incidence rates and IRRs will be calculated by weighting the incidence or IRR of each stratum (defined by propensity score decile and calendar year) by the amount of Jardiance® (Empagliflozin) person-time within the stratum - An additional analysis will further stratify the IRRs by categories of insulin use at the index date - Additional sensitivity analyses will be performed to evaluate potential for bias and confounding. 		

Name of company: [REDACTED]			
Name of finished medicinal product: Jardiance®			
Name of active ingredient: Empagliflozin			
Protocol date: 16 Oct 2017	Study number: 1245.149	Version/Revision: 3.0	Version/Revision date: 23 Sep 2019
Milestones:	Data collection will start in Q3 2018; The Final report will be produced using data through 12 months from the start of use of Empagliflozin or DPP4I index date (currently planned study period data collection from Q3 2018 – Q4 2020).		

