6. MILESTONES

Milestone	Planned Date
IRB/IEC approval	Q2 2018 – Q3 2018
Start of data collection (trial data) FPI	Q3 2018
Recruitment Period (LPI)	Q4 2019
Ramadan Month 2019	May 5th, 2019 – June 4th, 2019 ±1-2 days
Ramadan Month 2020	April 23 rd , 2020 – May 23 rd , 2020 ±1-2 days
Interim Progress Report to SFDA (as per the Saudi FDA templates)	Q4 2018, Q2 2019, Q4 2019, Q2 2020, Q4 2020
End of data collection (LPV)	Q4 2020
Final report of study results: CSR preparation	Q2 2021

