During the statistical analyses, analyses will be stratified by treatment complexity (mono vs. dual vs. triple therapy) and by calendar time of treatment initiation. Prior or current use of insulin is allowed; an additional stratified analysis by insulin use is planned. Propensity scores based on information prior to the index date will be used to account for potential confounding.

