9.7.2 Main analysis using stratification

For the incident users of Empagliflozin along with their respective comparators, analysis will be performed using the “as-treated” (AT) approach. This corresponds to censoring individuals who discontinue use of the index drug, i.e. who either switch from the index drug to any other of the index drugs (Empagliflozin or DPP-4 inhibitor) during follow-up or who stop using the index drug. The AT approach is considering index periods.

For each event of interest, ketoacidosis, severe urinary tract infections, volume depletion, and dehydration, crude and adjusted incidence rates per cohort will be described and compared by means of incidence rate ratios (IRR). Incidence rates will be reported as point estimates and 95% confidence intervals (CIs). Crude incidence rates will be adjusted per 1,000 person-years. Per cohort and, where appropriate per stratum and/or subgroup, the number of person-years is the sum of length of index periods of all patients. Time to first event occurrence will be compared by means of hazard ratios and their 95% confidence intervals.

IRRs and hazard ratios are analysed using stratification. Strata are defined by PS quintiles. IRRs are investigated by means of a stratified Mantel-Haenszel analysis, while hazard ratios are investigated by means of a Cox regression, if proportional hazards can be assumed.

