4.2 Sample Size Rationale

The sample size of 1,500 patients is based on SFDA requirements. The aim is to achieve comparable group sample sizes of 750 patients each. However given the real-world design of this study this may not be possible.

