4.9.1 Analysis of Primary Endpoints

For each of the four target adverse events (DKA, volume depletion, dehydration, serious UTI) the primary endpoints are the incidence rates and times to first occurrence in the index period,

Statistical Analysis Plan (SAP)

Document Date: 17APR2019

Document Version: 1.0 Final

analysed within each PS-based stratum by logistic regression and proportional-hazards Cox regression, respectively. Time to first event occurrence will be compared using hazard ratios and their 95% confidence limits. The assumption of proportional hazards will be tested [Kleinbaum 2012].

Estimates for each stratum and respective variances will be averaged across strata to yield overall weighted estimates considering subclass weights [Austin 2010, Guo 2015].

The statistical analysis models will contain factors and covariates with a potential effect on the outcome. These may include the treatment-confounding candidates listed in section 4.9 above, and will include the season, i.e., the quarter of the calendar year of the index date, and other effects yet to be short-listed. Site may also be included as a candidate variable.

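### The SAP's season term carries no year, so Q3 and Q4 entrants of 2018 and 2019 share a level, and the calendar-time adjustment promised in the protocol is reduced

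*Protocol*

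**What the plan says.** The protocol handles calendar time in several places, and they do not agree.

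- Abstract (Variables), repeated in 9.3.4: "cohort members will also be classified by indicator variables on the calendar time of cohort entry (by quarter"). This promises a classification only.
- 9.3.2: "analyses will be stratified by treatment complexity (mono vs. dual vs. triple therapy) and by calendar time of treatment initiation". This promises an adjustment.
- Abstract (Data analysis): the summary Mantel-Haenszel IRRs are adjusted "for propensity score deciles and calendar year, among Empagliflozin new users versus DPP-4 inhibitor new users". The strata that weight the adjusted rates and IRRs, which are the main effect estimates, are "defined by propensity score decile and calendar year".
- 9.7.2, the main analysis in the body: "Strata are defined by PS quintiles". No calendar factor appears.

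SAP 4.9 lists the PS candidates and calendar time is not among them. Its strata are PS quintiles, with more strata if balance is poor. SAP 4.9.1 says the outcome models "will include the season, i.e., the quarter of the calendar year of the index date", and leaves room for further effects still to be chosen. SAP 4.9.2 analyses the Ramadan endpoints in the same way.

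Protocol section 6 puts the first patient in at Q3 2018, and its row "Recruitment Period (LPI") gives Q4 2019. The SAP is dated 17 April 2019. Protocol 3.0, which extended recruitment, is dated 23 September 2019.

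**The concern.** Season is a recurring four-level factor. It can absorb within-year effects such as heat. It cannot separate a patient who entered in Q3 2018 from one who entered in Q3 2019, and the same holds for Q4. If prescribing or event recording drifted over the 18 months of recruitment, that drift stays uncontrolled within those two seasons.

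Drift is plausible, since protocol 9.1 describes empagliflozin as newly marketed, but the documents give no evidence of it. The estimates at stake are the adjusted IRRs for all four outcomes, which the abstract calls the main effect estimates and defines with calendar year in the strata. The Ramadan analyses inherit the same coding.

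**Working it through.** The documents state no figure on this point, so there is none to reproduce. The check has two parts.

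**Coding.** Entry quarters from Q3 2018 to Q4 2019 are 2018 Q3, 2018 Q4, 2019 Q1, 2019 Q2, 2019 Q3 and 2019 Q4: six levels (5 df). Season has four levels (3 df). Q3 and Q4 each occur twice and are merged; Q1 and Q2 occur once and stay separate. If accrual is uniform (an assumption), 1500 × 4/6 = 1000 patients sit in merged levels and 500 do not.

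**Size of the possible bias under a true IRR of 1.** All inputs here are assumptions, because the documents give none:

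- equal person-time in each of the six quarters;
- an empagliflozin share of 1−s in the 2018 quarters, s in 2019 Q3 and Q4, and 50% in 2019 Q1 and Q2;
- an event rate in 2019 entrants R times that in 2018 entrants.

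*Inside one merged season.* Set person-time per quarter to 1. Each group then has person-time (1−s) + s = 1. Expected events are proportional to (1−s) + sR for empagliflozin and s + (1−s)R for DPP-4 inhibitors, so

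IRR = [(1−s) + sR] / [s + (1−s)R].

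*Pooled over the four seasons by Mantel-Haenszel.* Each season adds (events in one group × person-time in the other) / total person-time to the numerator and the denominator.

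- A merged season has total person-time 2 and adds [(1−s) + sR]/2 and [s + (1−s)R]/2. There are two of them.
- An unmerged season has total person-time 1 and adds 0.5R × 0.5 = 0.25R to both. There are two of these as well.

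Hence

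IRR = [(1−s) + sR + 0.5R] / [s + (1−s)R + 0.5R].

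Example, s = 0.6 and R = 2: inside a merged season (0.4 + 1.2)/(0.6 + 0.8) = 1.6/1.4 = 1.143; pooled (0.4 + 1.2 + 1.0)/(0.6 + 0.8 + 1.0) = 2.6/2.4 = 1.083.

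| Empagliflozin share, 2018 to 2019 | R | Inside merged season | Pooled |
|---|---|---|---|
| 50% to 50% | any | 1.00 | 1.00 |
| 45% to 55% | 1.25 | 1.02 | 1.01 |
| 45% to 55% | 1.5 | 1.04 | 1.03 |
| 45% to 55% | 2 | 1.07 | 1.04 |
| 40% to 60% | 1.25 | 1.05 | 1.03 |
| 40% to 60% | 1.5 | 1.08 | 1.05 |
| 40% to 60% | 2 | 1.14 | 1.08 |

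If the share fell instead of rising, the values are the reciprocals: for a 60% to 40% shift the pooled IRR is 1.725/1.775 = 0.97 at R = 1.25 and 2.4/2.6 = 0.92 at R = 2. With year-by-quarter coding every entry in the table becomes 1.00.

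Mantel-Haenszel over seasons stands in here for the SAP's regression with a season covariate inside PS strata. It shows the order of magnitude and is not a simulation of the planned model.

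**The case against.** The strongest counter-argument is the enrolment quota. The protocol repeatedly asks each site to recruit similar numbers in both groups within a given timeframe, by assigned blocks. If that holds, the treatment mix is the same in both years and merging them causes no bias. This stands, with one limit: the quota balances headcounts at entry, while the as-treated IRR uses person-time. If discontinuation differed by drug and by entry year, the person-time mix could still diverge. Nothing in the documents says that it will.

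Second, the protocol body (9.7.2) stratifies by PS quintiles alone, so the SAP follows the body while departing from the abstract and 9.3.2. That also stands. It makes the mismatch one to reconcile across both documents, and does not remove it.

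Third, SAP 4.9.3 and part of SAP 4.10 are not visible in the public text, and SAP 4.9.1 allows further effects. A calendar-year term cannot be ruled out, but none is committed to in what can be read.

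A reader might also infer more than the documents support:

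- *That calendar adjustment is lost.* Season is a mandatory covariate, and Q1 and Q2 2019 keep their own levels.
- *That SAP 4.2 concedes the drift.* Its sentence "However given the real-world design of this study this may not be possible" concerns overall group sizes of 750 each. Unequal totals with a stable ratio over time cause no calendar confounding.
- *That the SAP became outdated through the recruitment extension.* The SAP does predate protocol 3.0, but the previous end of recruitment is not in the documents, so it is unknown whether the overlap arose then or already existed.
- *That Ramadan exposure is misassigned.* Ramadan periods are set by actual dates (SAP 2.2 and 4.4), not by season. Which Ramadan a patient meets matters for the comparison only if the entry mix differs by group.

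**Conclusion.** The point holds as a limited gap. Followed as written, the visible SAP leaves any 2018-versus-2019 difference within Q3 and Q4 entrants uncontrolled, contrary to protocol 9.3.2 and the abstract, and the protocol is itself inconsistent because 9.7.2 has no calendar factor.

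The effect depends on a shift in treatment mix that the quota is meant to prevent. Under the stated assumptions, a 40% to 60% shift takes a null IRR to about 1.03 to 1.08 pooled, a 45% to 55% shift to about 1.01 to 1.04, and balance leaves it at 1.00. The range of 1.05 to 1.14 applies only inside a merged season and should not be read as the study-level bias. The size of the shift and of R are illustrative; the documents support neither value. This is a low-priority correction, worth making because it is nearly free.

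**What to change.** - **SAP 4.9:** add calendar quarter of entry including year (six levels, 2018 Q3 to 2019 Q4) to the PS candidates, or season plus calendar year if data are sparse. State that it stays in the PS model whatever its p-value, since the 0.25 screen and backward elimination could otherwise remove it. Record this as a deliberate exception to the selection rule in protocol 9.7.1 and SAP 4.9. Show its balance by PS stratum.
- **SAP 4.9.1:** define the season term to include year. This raises it from 3 to 5 df in the outcome models. If events are too few for that (protocol 9.9 already warns that numbers may be low for ketoacidosis), leave season unchanged there and rely on the PS.
- **Alignment:** make the protocol abstract (Data analysis), protocol 9.3.2, protocol 9.7.2 and SAP 4.9.1 say the same about whether calendar time enters the PS, the strata or the outcome model.

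The cost is wording and one variable derived from the index date, which is already collected. The downside is up to five extra terms in a PS model fitted on about 1500 patients.

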9.7 DATA ANALYSIS

Details of all analyses and variables specification will be defined in a separate SEAP.

Patients are grouped according the exposure to either Empagliflozin or DPP-4 inhibitors. Data will be analysed per group. Let the index period define the time from index date to the end of treatment as defined in [section 9.3.2](#) by current use, and the follow-up period the time from index date to the end of observation as defined in [section 9](#). Incidences will be derived if events of interest occur in the respective period. The main analysis will consider index periods only, a secondary analysis will consider only the time of the index period in the month of Ramadan in every year, while sensitivity analyses will consider respective follow-up periods, overall or during Ramadan only. Times from index date to first occurrence will also be determined per event of interest and described by means of Kaplan-Meier estimates and median times with 95% confidence intervals, where appropriate.

All individual data will be listed and described per group by means of summary tables presenting frequency counts and percentages for categorical data and arithmetic means, standard deviations, medians, minimum and maximum values for continuous data. Baseline is defined as the last observation on or before the index date.

For the assessment of the primary and secondary objectives, the main data analysis will be conducted in two stages:

- 1) Construction of the PS by modelling the exposure to Empagliflozin vs. DPP-4 inhibitor;
- 2) Estimation of the effect of exposure to Empagliflozin on the risk of ketoacidosis, severe urinary tract infections, volume depletion and dehydration compared to those exposed to DPP-4 inhibitor.

Propensity score stratification will be the primary method to control for the confounders in the analysis phase. The stratification will divide the study population in several groups (max. 5 groups) based on their propensity score value. Propensity score matching will also be used as secondary method in the analysis phase.

All statistical tests will be conducted with a two-sided significance level alpha of 0.05 and all analyses will be conducted using SAS statistical analysis software version 9.4 (SAS Institute, Inc., Cary, NC) or later.

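### The protocol defines its main adjusted incidence rate ratio in two incompatible ways (strata and weights), and the visible SAP does not settle which one applies

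*Protocol*

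**What the plan says.** **Protocol, Abstract (Data analysis).** The status of the estimate is clear: "Adjusted IRRs for each of the outcomes will be the main effect estimates of interest". Its construction is given twice. One bullet describes "Summary IRRs, after adjusting (via stratified Mantel-Haenszel analysis) for propensity score deciles and calendar year". The next obtains adjusted rates and IRRs by "weighting the incidence or IRR of each stratum (defined by propensity score decile and calendar year"), with weights set "by the amount of Jardiance® (Empagliflozin) person-time within the stratum".

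**Protocol 9.7, 9.7.1 and 9.7.2.** Section 9.7 says "The stratification will divide the study population in several groups (max. 5 groups"). Section 9.7.1 uses quintiles. Section 9.7.2, headed as the main analysis, says "Strata are defined by PS quintiles" and investigates IRRs by stratified Mantel-Haenszel. None of the three has a calendar-year stratum or empagliflozin person-time weights.

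**SAP.** Section 4.9 starts from five PS quintiles but raises the number of strata until covariate balance is judged reasonable. Section 4.9.1 fits logistic and Cox regressions within each stratum and averages the results with subclass weights that it does not define. Its outcome models also take in calendar time: "and will include the season, i.e., the quarter of the calendar year of the index date". Section 4.10 says that stratified Mantel-Haenszel will be applied as the protocol planned. The rest of 4.10 is redacted, and 4.9.3 is not visible.

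**The concern.** This is a safety study requested by the regulator, and the conflict concerns its named main estimate for all four primary outcomes. An analyst following the abstract, one following 9.7.2 and one following SAP 4.9.1 could each report a different IRR from the same data, and no visible rule says which one counts. Of the two abstract constructions, the average of stratum IRRs needs a comparator event in every stratum, which is unlikely for outcomes such as ketoacidosis. Protocol 9.9 itself concedes that patient numbers may be low for that outcome.

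**Working it through.** The plan gives no figure to reproduce: the sample size is set by the regulator, and no event rate or effect size is stated. The check is a comparison of the texts, followed by illustrations on stated assumptions.

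**1. The definitions side by side**

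| Source | PS strata | Calendar time | Combination across strata |
|---|---|---|---|
| Abstract, summary IRR | deciles | calendar year | Mantel-Haenszel |
| Abstract, adjusted IRR | deciles | calendar year | empagliflozin person-time |
| Protocol 9.7 to 9.7.2 | at most 5; quintiles | none | Mantel-Haenszel |
| SAP 4.9, 4.9.1 | quintiles, may increase | season, as model covariate | undefined subclass weights |
| SAP 4.10 (visible part) | not stated | not stated | Mantel-Haenszel |

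Ten deciles cannot meet a maximum of five groups. Nor can a stratum count that may rise above five. The weights conflict inside the abstract as well as between the abstract and the body.

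**2. Size of the strata**

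Inputs: 750 patients per group (Protocol 9.5); 12 months of follow-up (9.1), so at most 750 person-years per group; entry from Q3 2018 to Q4 2019 (section 6), so two entry years. An even spread over strata is assumed.

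- Quintiles: 750 / 5 = 150 person-years per group per stratum.
- Deciles by two entry years: 750 / 20 = 37.5.
- If calendar year means 2018 to 2020: 750 / 30 = 25.

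As-treated censoring can only lower these figures.

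**3. Strata with no comparator event**

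Under a Poisson model, P(no comparator event) = exp(-rate × person-years). A stratum with none has no defined IRR. The rates are assumptions.

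| Comparator rate per 1,000 person-years | 5 strata | 20 strata | 30 strata |
|---|---|---|---|
| 1 | 0.86 | 0.96 | 0.98 |
| 5 | 0.47 | 0.83 | 0.88 |
| 10 | 0.22 | 0.69 | 0.78 |

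For example, at 10 per 1,000 with 20 strata, exp(-0.375) = 0.687. The chance that all 20 stratum IRRs exist is (1 - 0.687)^20, about 8e-11. At 50 per 1,000 it is (1 - exp(-1.875))^20 = 0.036. Averaging stratum IRRs is fragile even with quintiles: at 10 per 1,000, (1 - 0.223)^5 = 0.28.

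Mantel-Haenszel, sum(E·Td/T) / sum(D·Te/T), needs only one comparator event in a stratum with person-time in both groups. Here E and D are the empagliflozin and comparator events, Te and Td the person-times, and T = Te + Td. The standardised ratio, sum(E) / sum(Te·D/Td), also survives empty strata, if every stratum has comparator person-time and at least one comparator event occurs overall.

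**4. Do the two weightings agree?**

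Assumed example: five strata of 300 person-years, empagliflozin shares 0.20, 0.35, 0.50, 0.65 and 0.80, comparator rate 20 per 1,000.

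- IRR of 2 in every stratum: both give 2.0.
- IRR rising 1, 1.5, 2, 2.5, 3: Mantel-Haenszel 12.3 / 6.15 = 2.0; empagliflozin person-time 1,725 / 750 = 2.3.
- IRR falling 3 to 1: Mantel-Haenszel 2.0; empagliflozin person-time 1,275 / 750 = 1.7.

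**5. Five against ten strata**

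Assumed: true IRR 1, one normal confounder shifted 0.5 SD between groups, log rate 1.0 per SD. The crude IRR is exp(0.5) = 1.65. In a large simulation the Mantel-Haenszel IRR is about 1.09 with five strata and about 1.045 with ten.

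**The case against.** The strongest reply is that the abstract is the outlier. Protocol 9.7 leaves analysis detail to a separate plan. Sections 9.7.1, 9.7.2 and SAP 4.9 all start from quintiles, and 9.7.2 and SAP 4.10 both name Mantel-Haenszel. The SAP is dated 17 April 2019, before the planned end of recruitment, and its trigger for adding strata is covariate balance, not outcomes. This weakens any suggestion of a choice between deciles and quintiles made after seeing results. It does not remove the contradiction: the abstract of protocol version 3.0 still carries the other definition, and SAP 4.9 and 4.9.1 depart from 9.7 and 9.7.2.

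The number of strata is also a small matter beside the imprecision. At 10 per 1,000 and IRR 1, each group expects 7.5 events. The standard error of the log IRR is sqrt(2/7.5) = 0.516, and the 95% interval runs from about 0.36 to 2.75. A shift from 1.09 to 1.045 is slight against that. This stands. What carries the point is the undefined main estimate and the weights.

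Three stronger readings are tempting, and the documents do not support them:

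- *Protocol 9.3.2 gives a third set of strata for the main IRR.* It says "analyses will be stratified by treatment complexity (mono vs. dual vs. triple therapy) and by calendar time of treatment initiation", but it names no estimate and does not cross these factors with the PS strata. SAP 4.9.4 makes treatment complexity a descriptive subgroup.
- *The abstract's analysis as a whole cannot be computed for rare outcomes.* Only averaging stratum IRRs fails in this way. The abstract also offers Mantel-Haenszel and weighting of stratum incidences.
- *The SAP makes no adjustment for calendar year at all.* That rests on reading season as pooling the same quarter of 2018 and 2019. The wording invites this reading but does not compel it, and Protocol 9.3.4 classifies patients by quarter of entry.

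**Conclusion.** The point holds. The protocol gives two incompatible definitions of its main effect estimate: decile-by-year strata with empagliflozin person-time weights, and at most five PS groups with Mantel-Haenszel. The visible SAP adds an open-ended number of strata and undefined weights. A clarification in the redacted part of SAP 4.10 or in the unseen 4.9.3 cannot be excluded, but the protocol would still contradict itself.

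The textual conflict needs no assumption. The sizes do: the event rates, even spread, full follow-up, PS shares and confounder strength are all illustrative and not from the documents. On those terms, one written rule (averaging stratum IRRs) fails in most cells at 10 per 1,000 person-years or below, and the choice of weights moves the IRR by 0.3 in either direction when it varies between 1 and 3 across strata. Mantel-Haenszel remains usable in sparse strata, but not without any comparator event: at 1 per 1,000, exp(-0.75) = 0.47 is the chance of none at all.

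**What to change.** State one primary estimate, in the same words, in the protocol abstract, 9.7 to 9.7.2 and SAP 4.9 and 4.9.1: the person-time Mantel-Haenszel IRR over PS quintiles, as 9.7.2 already has it. Then:

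- Delete the weighting of stratum IRRs from the abstract. Keep empagliflozin person-time weights only for standardised rates.
- In SAP 4.9, bring the rule that adds strata into line with the maximum of five. In 4.9.1, replace the within-stratum logistic estimates and undefined subclass weights with the Mantel-Haenszel IRR, and keep stratified Cox regression for the hazard ratio as in 9.7.2.
- Name PS deciles as one sensitivity analysis.
- Say whether calendar time of entry is adjusted for. If it is, use the year and quarter of entry (six levels, Q3 2018 to Q4 2019), making the quarter classification in 9.3.4 explicit, rather than season alone.

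The cost is a protocol and SAP amendment, with no new data or patients. It is more than an edit to the abstract, because it changes the SAP's balance rule and its stated model for incidence. The statistical price is slightly more residual confounding with quintiles, which the decile analysis would show.
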